## 9.6. Physical and Neurological Examination

The physical and neurological examination results, graded as normal or abnormal will be summarized using counts and percentages at visits described in Table 2 . Denominator for the percentages will be the number of subjects in the treatment group.

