
Safety
	
All safety analyses will be conducted on the Safety Population, which will be defined as all participants who were randomized and had at least one treatment performed.
 
When evaluating changes in safety parameters, Baseline will be defined as the last measurement prior to the first treatment.
 
For physical examination, concomitant medications, hematology and blood chemistry, ECG assessments, shifts from baseline in categorization of results (e.g. normal/abnormal or above/below normal range) will also be summarized.
 
All continuous data obtained in this study and documented in the electronic case report forms (eCRFs) will be listed and tabulated with descriptive group statistics (n, mean, standard

	deviation, median, minimum, maximum). For discrete data, counts and percentages will be summarized.
Biomarkers	CSF and/or serum or blood samples will be analyzed for the concentration of biomarkers and their relationship to efficacy outcomes. In addition, relationships between neurotropic factors, inflammatory markers and clinical outcomes will be evaluated to determine if any biomarkers can be predictive to treatment outcome or prognostic to disease progression.

TABLE OF CONTENTS

STUDY SYNOPSIS	6
TABLE OF CONTENTS	13
ABBREVIATIONS.....	15
1. CLINICAL STUDY PROTOCOL.....	17
1.1 INTRODUCTION	17
1.1.1. COVID-19 Pandemic.....	18
1.2 STUDY OBJECTIVES	19
1.2.1. Primary objectives	19
1.2.2. Secondary Objectives	19
1.3 INVESTIGATIONAL PLAN.....	20
1.3.1 Overall Study Design and Plan.....	20
1.3.2 Study Schematic	21
1.3.3 Treatment Plan.....	22
1.3.4 Blinding and Randomization	22
1.3.5 Duration of study	23
1.3.6 Discussion of Dose	23
1.3.7 Discussion of Study Design, Including Choice of Control Group	24
1.4 PATIENT POPULATION.....	24
1.4.1. Inclusion Criteria	24
1.4.2. Exclusion Criteria	25
1.5. STUDY ASSESSMENTS	26
1.5.1. Anticoagulation therapy.....	26
1.5.2. CSF and Blood collection for assessments of Biomarkers.....	27
1.5.3. Genetic Analyses	27
1.5.4. Clinical Laboratory Safety Tests	27
1.5.5. Physical Examinations, Vital Signs, and Electrocardiograms.....	27
1.5.6. Pre-transplantation Visits.....	28
1.5.5. Transplantation Visits.....	30
1.5.6. Post transplantations follow-up	35
1.5.7. Safety Follow-Up.....	36
1.5.8. Lost to Follow-Up	36
1.6. INVESTIGATIONAL PRODUCT INFORMATION	37
1.6.1. General Information.....	37
1.6.2. NurOwn® (MSC-NTF cells) Product Characteristics.....	37
1.6.3. Treatment Compliance.....	38

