1.9.3.5. Safety analyses

All safety analyses will be analyzed in the Safety Population.

All AEs will be coded to System Organ Class (SOC) and Preferred Term (PT) using the Medical Dictionary for Regulatory Activities (MedDRA®). The number of treatment-emergent adverse events (TEAEs) and the number of participants with any TEAEs (along with percentages) will be tabulated by SOC and PT within each SOC by treatment group and over treatment groups. To count the number of participants with any TEAEs, a subject who experiences multiple TEAEs within the same SOC will be counted only once for that SOC (whether or not the TEAEs are coded to the same PT). A subject who experiences multiple TEAEs coded to the same PT within the same SOC will be counted only once for that particular PT. In the summary, SOC and PT's will be listed in descending alphabetical order.

A TEAE is an AE that occurs for the first time after initiation of treatment or if had occurred prior to treatment, worsens in severity after initiation of treatment.

Separate summaries will be provided for the following categories of AEs:

- TEAEs
- TEAEs by severity
- Treatment-related TEAEs
- Serious TEAEs

When evaluating changes in safety parameters, Baseline will be defined as the last measurement prior to transplantation (i.e., prior to treatment).

Physical examination, neurological examination, hematology, serum chemistry, vital signs and concomitant medications will be summarized using descriptive statistics (n, mean, standard deviation, median, minimum, and maximum) if the data is continuous and using counts and percentages if the data is discrete. Shifts from baseline in categorization of results (e.g. normal/abnormal or low/normal/high) will also be summarized.

All continuous data obtained in this study and documented in the eCRFs will be listed and tabulated with descriptive group statistics (n, mean, standard deviation, minimum, median, maximum). For discrete data, counts and percentages will be summarized.

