#### 3.2.1.2. Safety

Safety endpoints include adverse events (AEs), changes in physical and neurological examination findings, laboratory evaluation (i.e. hematology, blood biochemistry, serum pregnancy test, urinalysis, coagulation test), vital signs, ECG assessment, suicidal ideation measured by Columbia-Suicide Severity Scale (C-SSRS) and requirement of concomitant medications.

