### 6.1. General Summary Table and Individual Subject Data Listing Considerations

Summary tables and listings will include a “footer” providing explanatory notes that indicate as a minimum:

1. Date and time of output generation.
2. SAS program name, including the path that generates the output.
3. Any other output specific details that require further elaboration.
4. Page number in the format of Page X of Y

Summary tables will also include reference(s) to the subject data listing(s) that support the summary data.

In general, summary tables will be organized with respect to the 2 treatment groups, NurOwn® and Placebo. An overall total column may be included, where appropriate.

For this study, the order of drug presentation will be the investigational drug NurOwn® first followed by placebo.

The summary tables will clearly indicate the number of subjects with non-missing data along with an indication of the number of subjects with missing data.

If no data exist for any subjects for a given Table or Listing “No Data to display” will be displayed.

Summary tables for medications and medical conditions and AE verbatim (reported) terms are coded to preferred terms (PT) and body/organ systems are coded per standard dictionaries mentioned in [Section 6.3](#).

All data collected in the study will be presented in individual Subject Data Listings (unless agreed to with the agency to not create certain listings e.g. Laboratory listings, which tend to be very large). All listings will include subject ID and treatment group (group). Where applicable, listings will also include visit number, visit date, and days relative to the initiation of treatment.

When missing or partial dates are imputed, the listings will display both the missing or partial dates as well as the imputed dates.

Any data derived for analyses will also be included with the raw data in the listings and flagged as derived data.

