#### 6.4. Data Presentation Conventions

Continuous variables (e.g. age) are summarized using descriptive statistics (the number of subjects with available data, the mean, standard deviation (SD), first quartile (Q1), median, third quartile (Q3), minimum and maximum). Categorical variables (e.g. race) are summarized using counts and percentages. Percentages are calculated using the total subjects per treatment group with available data (overall or within relevant subgroup when appropriate). Summaries for discrete variables will include frequencies and percentages. Denominators used for computation of percentages will be indicated in footnotes on tables.

The following conventions will be applied to all data presentations and summaries.

- For continuous variables, all mean, Q1, median and Q3 values are formatted to one more decimal place than the measured value. Standard deviation values are formatted to two more decimal places than the measured value. Minimum and maximum values are presented with the same number of decimal places as the measured value. This rule may be modified to fit data in a given Table as long as the data displays relevant decimal places for interpretation of results.
- For categorical variables, the number and percentage of responses are presented in the form XX (XX.X%) where the percentage is in the parentheses and will be rounded to one decimal place.
- Date variables are formatted as DDMMYYYY for presentation. Time is formatted in military time as HH:MM for presentation.
- Wherever possible, data will be center, decimal or left aligned as appropriate to best display the data and column headers. Parenthesis will also be aligned appropriately for best display. This will be detailed in the mock shells.
- P-values, if applicable, will be presented to 3 decimal places. If the p-value is less than 0.001 then it will be presented as <0.001. If the rounded result is a value of 1.000, it will be displayed as >0.999.
- Unless otherwise stated, any statistical tests performed will use 2-sided tests at the 5% significance level.

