#### 6.5. Analysis Populations

During the conduct of this study starting in February 2020 the pandemic due to COVID-19 impacted the US and some of the subject in-clinic visits for intrathecal administrations, efficacy or safety assessments were either delayed or cancelled. As of finalization of this SAP the COVID-19 pandemic is still ongoing and its impact is yet unknown. All subjects who continued in the study and were intended to receive treatments are receiving them with sometimes longer duration between visits due to travel restrictions, manufacturing and clinical site constraints. Phone visits were conducted as close to the planned visits to determine if subjects had AEs or there were changes to any CMs. Since the ALSFRS-R is validated to be performed over the

phone, these were conducted as close to the planned visits as possible. Protocol deviations due to COVID-19 are being captured and will be summarized in the clinical study report (CSR).

Prior to locking the database and unblinding the study, the impact of treatment delays due to manufacturing scheduling or due to COVID-19 will be assessed on the data collected and additional modifications to the populations below may be made. In addition, sensitivity analyses may be added including/excluding data collected that may have been impacted due to COVID-19.

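### SAP 9.6 drops the shift-from-baseline summary that the protocol promises for physical and neurological examinations, so its table cannot show how many participants became newly abnormal

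*SAP*

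**What the plan says.** - **Protocol 1.9.3.5 (Safety analyses)** names physical and neurological examination among the parameters to be summarised, and then adds: "Shifts from baseline in categorization of results (e.g. normal/abnormal or low/normal/high) will also be summarized".
- **Protocol synopsis, Safety**, makes the same promise for a list that includes the physical but not the neurological examination: "For physical examination, concomitant medications, hematology and blood chemistry, ECG assessments, shifts from baseline in categorization of results".
- **SAP 3.2.1.2** gives the safety endpoint as "changes in physical and neurological examination findings".
- **SAP 9.6** has two sentences. The first sets the method: "The physical and neurological examination results, graded as normal or abnormal will be summarized using counts and percentages at visits" in SAP Table 2. The second sets the denominator: "Denominator for the percentages will be the number of subjects in the treatment group".
- **SAP 6.4**, the general convention, differs: "Percentages are calculated using the total subjects per treatment group with available data". **SAP 6.1** requires summary tables to carry an "indication of the number of subjects with missing data".
- **SAP 6.5** reports that during the pandemic "some of the subject in-clinic visits for intrathecal administrations, efficacy or safety assessments were either delayed or cancelled".

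**The concern.** The endpoint is a change within participants, and the protocol commits to tabulating it. SAP 9.6 tabulates only the state of each arm at each visit. Visit 6 is among those visits, so a reader can see whether the abnormal count rose or fell overall, but not how many participants moved from normal to abnormal.

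The examinations are also the exception among the SAP's safety measurements. Laboratory data (9.4) get change from baseline and shift tables, including worst post-baseline. Vital signs (9.5) and ECG (9.7) get change from baseline. The C-SSRS (9.8) gets shift tables.

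Two details of 9.6 blur even the net change:

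- It refers only to the visit-level Table 2. SAP Table 3 schedules a physical examination both before injection and about 24 hours after it at Visits 6, 9 and 11, and 9.6 does not say which is counted.
- With the whole arm as denominator, a participant who was not examined counts as not abnormal.

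At stake is the number of participants per arm with a new examination abnormality that was not reported as an adverse event.

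**Working it through.** The plan states no figure for this point, so there is none to reproduce. The documents give no abnormality rates either, so the numbers below are bounds or illustrations under stated assumptions, not predictions.

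**1. Is the shift supplied elsewhere?** Sections 9 to 9.8 of the SAP contain no baseline-by-visit table for either examination. Section 9 speaks of clinically relevant changes in them and promises by-subject listings, but sets no tabulation of change.

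**2. What the per-visit counts leave open at one visit.** Let N participants be examined at both times, with b abnormal at baseline and v abnormal at the visit. The number newly abnormal lies between max(0, v − b) and min(v, N − b). Assume N = 100, from the planned size of about 100 per arm.

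| b | v | Lowest | Highest |
|---|---|---|---|
| 20 | 20 | 0 | 20 |
| 30 | 30 | 0 | 30 |
| 30 | 40 | 10 | 40 |
| 50 | 50 | 0 | 50 |
| 60 | 60 | 0 | 40 |
| 80 | 80 | 0 | 20 |
| 80 | 85 | 5 | 20 |
| 90 | 90 | 0 | 10 |
| 95 | 95 | 0 | 5 |
| 100 | 100 | 0 | 0 |

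Two arms with identical rows under 9.6 can differ by the width of the range. The upper end requires participants who were abnormal at baseline to become normal. If abnormalities never resolve, the newly abnormal number is exactly v − b and the counts suffice. The range narrows to nothing as b approaches N.

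**3. What they leave open over the whole study.** Suppose 3 participants are newly abnormal at each of K time points. The number ever newly abnormal runs from 3 (the same people each time) to 3K (different people each time, if that many were normal at baseline).

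- SAP Table 2, Visits 7 to 14: K = 8, so 3 to 24.
- Adding the three 24-hour physical examinations: K = 11, so 3 to 33.
- Protocol Table 1 has no physical examination at Visit 7: K = 7, so 3 to 21, or K = 10 with the 24-hour examinations, so 3 to 30.

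Thus even the exact number newly abnormal at each visit would not give the any-visit total. That needs a worst-post-baseline row.

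**4. Effect of the denominator.** Assume 60% abnormal among those examined and a fraction m not examined. The percentage shown under 9.6 is 60% × (1 − m):

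- m = 0.10: 54%
- m = 0.20: 48%
- m = 0.30: 42%

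**The case against.** The strongest case on the other side is that little is lost.

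- **Adverse events.** Protocol 1.8.1.1 brings observations on physical examination within the adverse event definition, and SAP 9.1.1 tabulates treatment-emergent events by arm. This stands, and it limits the loss to new abnormalities not reported as events.
- **Listings.** Every safety parameter is listed by subject, so the count could be made by hand. True, but a listing is not the summary the protocol promised.
- **Ceiling.** All participants have diagnosed ALS with documented decline, so an overall neurological grade may be abnormal at baseline for nearly everyone. This stands: the bound is 0 to 5 at b = 95.
- **Extreme bounds.** The upper ends need abnormal findings to resolve, which fits a progressive disease poorly. This is fair for persistent neurological signs. It is less so for the physical examination, where transient findings are possible.
- **Denominator.** The preamble to SAP section 6 allows individual sections to set data-specific rules, so 9.6 does not contradict 6.4, and the number missing must be shown. Both are correct. A reader can recover the percentage among those examined, but the printed percentage still falls when examinations are missed.
- **Timing.** SAP 6.6 fixes baseline as the last measure before first treatment, which settles which Visit 6 examination is the baseline one. It does not settle which physical examination 9.6 counts at Visits 6, 9 and 11. The neurological examination is unaffected, as Table 3 schedules it only before injection.

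These points reduce the importance of the gap. None of them supplies the missing table.

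**Conclusion.** The concern holds. SAP 9.6 omits a summary that protocol 1.9.3.5 commits to, and the table it plans cannot give the number of participants newly abnormal, at one visit or at any visit. The all-participants denominator and the unspecified physical examination time point are lesser weaknesses of the same section.

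The effect is small and descriptive. The primary analysis, power, Type I error and adverse event reporting are untouched. How much information is lost depends on rates the documents do not give: it could be tens of participants per arm if baseline abnormality is moderate and findings come and go, and close to none if nearly all are abnormal at baseline or findings persist. The practical gain therefore lies mainly in the physical examination. The change should be made because the protocol promises the summary and it costs little.

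**What to change.** In SAP 9.6 add, by arm and for both examinations, normal/abnormal shift tables from baseline (as defined in SAP 6.6) to each post-baseline visit and to worst post-baseline, in the form SAP 9.4 already uses for laboratory data. The worst-post-baseline row goes slightly beyond the protocol's wording but answers the any-visit question.

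Show the physical examination about 24 hours after injection at Visits 6, 9 and 11 as a separate post-baseline time point. Use as denominator the participants with a baseline and the relevant post-baseline examination, and print the number missing.

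The cost is some SAP wording before database lock and a few descriptive tables from examinations already scheduled. Disease progression also produces new findings, so the tables must be read as a comparison between arms and not as a count of treatment effects.

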## 9.7. Electrocardiograms

Heart rate (HR) in beats per minute, QT interval in milliseconds, and QTcF (Fridericia’s formula) interval in milliseconds will be summarized using continuous descriptive statistics by treatment group at visits described in Table 2. QTcF (Fridericia’s formula) will be estimated by the following:

$$QTcF = \frac{QT}{(RR)^{1/3}} \quad \text{where } RR = 60/HR$$

Change from Baseline to each post-Baseline visit will be also summarized by treatment group. The number and percentage of subjects with changes in QTcF from Baseline of >30 msec and >60 msec as well as the number and percentage of subjects with QTcF values >450 msec will be tabulated at each post-treatment visit.

## 9.8. Columbia-Suicide Severity Rating Scale (C-SSRS)

Suicidal ideation and behavior will be assessed using the C-SSRS. The binary response, yes or no, will be categorized for each category. The suicidal ideation score will be defined as the maximum suicidal ideation category (1-5 on the C-SSRS) present at the assessment. In case of no ideation present, the suicidal ideation score will be kept as 0.

A “yes” answer at any time during treatment to any one of the five suicidal ideation questions (categories 1-5) on the C-SSRS will be categorized as “Suicidal ideation”. A “yes” answer at any time during treatment to any one of the five suicidal behavior questions (categories 6-10) on the C-SSRS will be categorized as “Suicidal behavior”. A “yes” answer at any time during treatment to any one of the ten-suicidal ideation and behavior questions (categories 1-10) on the C-SSRS will be categorized as “Suicidal ideation or behavior”.

Patients with any suicidal ideation, suicidal behavior, and suicidal ideation or behavior will be tabulated by treatment at screening (lifetime measure), during the pre-transplantation period and during the post-transplantation period. Shift tables showing changes in suicide ideation scores from screening (lifetime measure) to worst at Baseline (pre-transplantation period) and from Baseline to worst post-transplantation will also be provided. Data will be reported as available without data imputation.

## 10. BIOMARKER AND GENETIC ANALYSIS

CSF and/or serum samples will be analyzed for the concentration of neurotropic factors and inflammatory markers, markers related to neurobiological processes and neuropathology and miRNAs, collectively referred to as biomarkers, and their relationship to efficacy outcomes at

each visit. In addition, relationships between neurotrophic factors, inflammatory markers, neuro-related biomarkers, miRNA expression and clinical outcomes will be evaluated to determine if any biomarkers can be predictive to treatment outcome or prognostic to disease progression. Correlation of all biomarkers with clinical endpoints (ALSFRS-R and SVC) will be explored.

A list of pre-specified biomarkers of interest which were identified through the preceding Phase 2 clinical trial and/or in different studies through the literature include: VEGF, HGF, LIF, MCP-1, SDF-1, CHIT-1, CHI3L1, Caspase-3, NfL, NfH, PDGFRb, TGF $\beta$ , IL-17, IL-37, GPNMB, miR-146, miR-132, miR-206.

Data available, even if partial, will be summarized either by descriptive statistics (continuous data) or by counts and percentages (binary data), and by treatment group.

CSF and blood samples are collected at multiple Visits, one prior to the first treatment and 6 times thereafter (See schedule of assessments).

Analyses will explore the following overall correlations by treatment groups:

- Between neurotrophic factors (NTFs) and inflammatory markers in CSF and serum.
- Between all biomarkers vs. the ALSFRS-R overall score
- Between all biomarkers vs. the ALSFRS-R slope (pre-treatment and post-treatment)
- Between Change in all biomarkers vs. change in ALSFRS-R overall score (from baseline).
- Between Change in all biomarkers vs. change in ALSFRS-R slope
- Between biomarkers vs. the SVC score, as well as the change in biomarker vs. change in SVC.
- To study whether response to NurOwn® treatment correlates with specific ALS genetic mutations or gene variants related to ALS

Genetic testing will include the following genes- ANG, ANXA11, ARHGEF28, C9orf72, DH13, CHGB, CX3CR1, FUS, GRN, HNRNPA1, HNRNPA2B1, KIF5A, MAPT, OPTN, PFN1, PSEN1, PSEN2, SETX, SOD1, SQSTM1, TARDBP, TBK1, TMEM106B, UNC13A, VAPB, VCP

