1.9.3.6. Biomarker Analysis

CSF and/or serum or blood samples will be analyzed for the concentration of biomarkers and their relationship to efficacy outcomes at each visit. In addition, relationships between neurotropic factors, inflammatory markers, miRNA expression, T regulatory cells and clinical outcomes will be evaluated to determine if any biomarkers can be predictive to treatment outcome or prognostic to disease progression. Analyses will be detailed in the SAP.

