### 3.2.2. Secondary Efficacy Endpoints

The key secondary efficacy endpoints will be tested sequentially -in the following order:

- To evaluate the efficacy of NurOwn® (MSC-NTF cells) vs. placebo as measured by the proportion of participants whose disease progression is halted or improved as measured by a 100% or greater improvement in post-treatment slope vs. pre-treatment slope in ALSFRS-R score at 28 weeks following the first treatment.
- To evaluate the efficacy of NurOwn® (MSC-NTF cells) vs. placebo as measured by improvements in ALSFRS-R score between baseline and 28 weeks following the first treatment using mixed effects repeated measures (MMRM).
- To evaluate the efficacy of NurOwn® (MSC-NTF cells) vs. placebo as measured by the combined analysis of function (CAFS), as measured by ALSFRS-R and survival, between baseline and 28 weeks following the first treatment.
- To evaluate the efficacy of NurOwn® (MSC-NTF cells) as compared to placebo, as measured by the change from baseline to 28 weeks in SVC using MMRM.

- To evaluate the efficacy of NurOwn® (MSC-NTF cells) as compared to placebo on tracheostomy-free survival
- To evaluate the efficacy of NurOwn® (MSC-NTF cells) as compared to placebo on survival.

In order to preserve Type I error, the primary efficacy endpoint and above key secondary efficacy endpoints will be tested sequentially.

Other secondary and exploratory efficacy endpoints evaluated will be:

- [REDACTED]
- [REDACTED]
- [REDACTED]
- [REDACTED]
- To evaluate biomarkers (neurotrophic factors [NTFs], inflammatory factors and cytokines), markers related to neurobiological processes and neuropathology and miRNAs) in the cerebrospinal fluid (CSF) before each treatment and at select time points as well as in serum samples throughout the study to evaluate their relationship to treatment with NurOwn® (MSC-NTF cells) as described in [Section 10](#) below.
- To study whether response to NurOwn® treatment correlates with specific ALS genetic mutations or gene variants related to ALS.
- Subgroup analyses will explore differences in treatment effect between key subgroups based on demographic, baseline severity and other clinically meaningful criteria.

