#### 4.3. Sample Size Considerations

Since the primary efficacy endpoint is based upon the percentage of responders who demonstrate a  $\geq 1.25$  points/month improvement in ALSFRS-R post treatment slope as compared to their pre-treatment slope, the sample size for this study is based upon estimation of the percentage of participants on NurOwn®, excluding slow progressors, who were responders at 12 weeks as observed in the previous Phase 2 BCT-001 US study.

At 12 weeks post-treatment 53% of NurOwn® (MSC-NTF cells) treated participants, excluding slow progressors, were observed to have an improvement in post-treatment slope using either the thresholds of  $\geq 1.0$  Points / month or  $\geq 1.5$  points / month.

The best estimate of the percentage of placebo participants who will be responders is based upon the % of responders among those receiving placebo at 24 weeks. At 24 weeks post-treatment, 17% of placebo participants were responders using the threshold of  $\geq 1.0$  Points / month and 0% using the threshold of  $\geq 1.5$  points / month.

Accounting for the longer duration of this study, missing data due to discontinuations and potentially fewer responders in the NurOwn® treated group we estimate the true percentage of responders who improve  $\geq 1.25$  point/month on NurOwn® to be 35% and on Placebo to be 15%. Utilizing a Chi-square test with Type I error rate of 0.05 two-sided and 90% power we would require 97 participants per treatment arm.

The true % of responders using the criteria of  $\geq 100\%$  improvement is also expected to be around 35% treated and 15 % placebo.

A sample size of approximately 100 participants per arm (approximately 200 participants total) will be randomized.

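### The visible text of SAP Section 10 plans only by-arm summaries and by-arm correlations, so it yields no between-arm estimate of biomarker change and no measure of whether a marker modifies the treatment effect

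*SAP*

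**What the plan says.** SAP Section 3.2.2 lists biomarkers under other secondary and exploratory endpoints. Samples are to be taken "throughout the study to evaluate their relationship to treatment with NurOwn® (MSC-NTF cells) as described in" Section 10. Section 10 adds a second aim: "to determine if any biomarkers can be predictive to treatment outcome or prognostic to disease progression". The protocol states the same aim in Section 1.9.3.6 and leaves the method to the SAP: "Analyses will be detailed in the SAP".

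Section 10 names two methods:

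- Descriptive statistics for continuous data, or counts and percentages for binary data, by treatment group.
- Correlations, introduced by "Analyses will explore the following overall correlations by treatment groups". They relate markers to each other, to ALSFRS-R score and slope (before and after treatment) and to SVC, and relate changes in markers to changes in those outcomes. The genetic item in the same list asks whether response to NurOwn correlates with variants and names no placebo contrast.

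The section lists 18 markers and 26 genes, with one sample before the first treatment and six after it. It names no between-arm difference, interval or test, no longitudinal model and no treatment-by-marker term. SAP 8.2 makes no multiplicity adjustment for other secondary or exploratory efficacy endpoints.

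**The concern.** The two aims need two different estimates.

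- **Relationship to treatment.** This is a between-arm contrast: how much marker change differs between NurOwn and placebo, and how precisely that is known.
- **Predictive or prognostic.** A prognostic marker tracks outcome whatever the treatment. A predictive marker is one along which the NurOwn-placebo difference in outcome changes. That second property is an interaction, and a correlation computed inside one arm does not estimate it.

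If Section 10 is followed as written, the report will hold two columns of means and two columns of correlation coefficients. Readers would have to judge by eye whether a marker moved with treatment and whether it identifies who benefits. With 44 candidates (18 + 26) and no rule for reading the two columns, a marker whose correlation is significant under NurOwn and not under placebo could be taken for a treatment-specific one.

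**Working it through.** **1. The plan's own figure.** The documents give no power or alpha for the biomarker analyses. The only design figure is for the primary endpoint: "Utilizing a Chi-square test with Type I error rate of 0.05 two-sided and 90% power we would require 97 participants per treatment arm". With p₁ = 0.35, p₂ = 0.15 and p̄ = 0.25:

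n = [1.960·√(2·0.25·0.75) + 1.282·√(0.35·0.65 + 0.15·0.85)]² / 0.20² = (1.200 + 0.764)² / 0.04 ≈ 96.4, so 97.

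The figure reproduces. It matters here only because it fixes the available size at about 100 per arm (SAP 4.3). Everything below uses assumed effect sizes.

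**2. A treatment effect on a marker leaves within-arm correlations unchanged.** Let the marker x have SD 1 and the outcome be y = 0.5x + error with SD 1 in both arms. The correlation is 0.5/√(0.25 + 1) = 0.45. Adding 0.5 SD to every NurOwn value of x does not alter it. In 3,000 simulated trials with 100 per arm, the mean correlations were 0.45 and 0.45, while a between-arm t-test detected the shift in 94% of runs.

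**3. Comparing two correlations is not a test of interaction.** A correlation depends on the residual spread as well as the slope: r = b/√(b² + s²) when x has SD 1.

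| Case | Placebo b, s | NurOwn b, s | Simulated r, placebo / NurOwn | Correlations differ (Fisher z) | Interaction significant |
|---|---|---|---|---|---|
| Prognostic only | 0.5, 0.7 | 0.5, 1.4 | 0.58 / 0.33 | 60% | 5% |
| Predictive | 0.4, 0.8 | 0.8, 1.6 | 0.44 / 0.44 | 4% | 60% |

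In the first row the marker has the same slope in both arms and the correlations differ. In the second the slope doubles and the correlations are the same.

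**4. How often a prognostic marker is significant in exactly one arm.** Assume n = 95 per arm (a little under 100, to allow for missing samples), the same true correlation r in both arms, and two-sided 0.05. Within-arm power is p ≈ Φ(atanh(r)·√92 − 1.96). The chance of significance in exactly one arm is 2p(1 − p).

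| r | atanh(r)·√92 | p | 2p(1 − p) |
|---|---|---|---|
| 0.2 | 1.945 | 0.494 | 0.50 |
| 0.3 | 2.969 | 0.844 | 0.26 |
| 0.4 | 4.063 | 0.982 | 0.035 |
| 0.5 | 5.269 | 0.9995 | 0.001 |

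The 50% at r = 0.2 is the mathematical maximum of 2p(1 − p). The problem is confined to weak or moderate correlations.

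**5. What a between-arm comparison could detect.** With 100 per arm, complete samples and two-sided 0.05, the detectable difference is (1.960 + 0.842)·√(2/100) = 0.40 SD at 80% power and (1.960 + 1.282)·√(2/100) = 0.46 SD at 90%. If 18 markers are each tested once at 0.05 and the tests are independent, the chance of at least one false positive is 1 − 0.95¹⁸ = 0.60.

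**6. What an interaction in the responder model could detect.** The planning rates imply about 35 + 15 = 50 responders in 200 participants. In a simulation with no marker effect on placebo, the interaction had about 21% power for an odds ratio of 1.5 per SD under NurOwn, and a little under 50% for an odds ratio of 2.0.

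**The case against.** The strongest reply has five parts.

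- **The arms are displayed.** Summaries by randomised group show means and spread side by side, and a reader can derive a difference from them. This stands. It would be too strong to infer that Section 10 cannot show a treatment effect on a marker. What is missing is a prespecified estimate with its uncertainty.
- **Placebo correlations are reported too.** A claim based on the NurOwn arm alone could be checked against the placebo column, and correlations with pre-treatment slope help identify prognostic markers. This also stands. A reader might infer that the plan calls a marker predictive when it is significant in one arm only, but the SAP states no such rule. The rates in step 4 show what would happen if someone read the tables that way. Nor is a significant within-NurOwn correlation for a prognostic marker a false positive: finding prognostic markers is half of the stated aim. What does not stand is that two correlations, even inspected together, answer the predictive question (step 3).
- **The work is exploratory.** It lies outside the sequential testing hierarchy, although protocol 1.2.2 lists biomarkers among the secondary objectives. This limits the weight of the point. It does not supply the missing method.
- **Subgroup analyses may cover it.** SAP 3.2.2 commits to exploring treatment effects in key subgroups but does not name biomarkers. The visible subgroup text in Section 8 mentions biomarkers and genetics only as optional and conditional on an imbalance between arms, with no interaction test. Parts of Section 8 are redacted or not visible, so a method there cannot be ruled out. Section 3.2.2, however, points to Section 10 for the biomarker method.
- **Interactions have little power.** This is correct, especially in the logistic model (step 6), and it shapes the fix.

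**Conclusion.** The point holds in a limited form. The visible text of Section 10 states two aims and gives methods that address them only informally: no between-arm estimate or interval for biomarker change, and nothing that measures whether the treatment effect varies with a marker or variant. The word overall in its list might mean pooled across visits or arms, but a pooled correlation would supply neither quantity.

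The size depends on the assumed correlation. With 95 per arm and a purely prognostic marker, significance in exactly one arm occurs in about 50%, 26% and 3.5% of trials at r = 0.2, 0.3 and 0.4. These are illustrations: the documents give no marker correlations, variances or sample completeness.

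No primary or key secondary result is affected, nor is the sample size. The change is still worth making before database lock, because models chosen after unblinding would weaken any biomarker claim.

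**What to change.** Amend SAP Section 10 as follows.

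1. **Treatment effect on markers.** For continuous markers, estimate the between-arm difference in change from the Visit 6 pre-dose value with an MMRM containing baseline value, treatment, visit and treatment-by-visit. Use the log scale where suitable, and report the ratio and 95% CI at each sampled visit. For binary markers, report the between-arm difference in proportions with a 95% CI.
2. **Prediction.** Assess it by the treatment-by-baseline-marker (or treatment-by-variant) interaction with its 95% CI, mainly in the ALSFRS-R change or slope model. Treat the logistic responder model as supportive, given about 50 expected responders. Describe variants that are too sparse to fit, without modelling them.
3. **Correlations and multiplicity.** Keep the by-arm correlations as descriptive and state that significance in one arm is not evidence of prediction. Label all marker and gene results as exploratory, or control the false discovery rate across the 18 markers and 26 genes.

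No new samples are needed. SAP 8.4 already specifies MMRM for ALSFRS-R and SVC, and SAP Section 2 allows additions before lock and unblinding. The cost is wording and some programming. The drawback is low power for interactions: fewer markers will look positive, and a wide interval should be reported as inconclusive, not as absence of prediction.
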